TITLE: Comparison Between Wound Vacuum Dressing and Standard Closure to Reduce Rates of Surgical Site Infections

NCT: NCT03021668

PI: [name]

DATE: 04/10/2018

JHM IRB - eForm A – Protocol

- Use the section headings to write the JHM IRB eForm A, inserting the appropriate material in each. If a section is not applicable, leave heading in and insert N/A.
- When submitting JHM IRB eForm A (new or revised), enter the date submitted to the field at the top of JHM IRB eForm A.

1. Abstract

- a. Provide no more than a one page research abstract briefly stating the problem, the research hypothesis, and the importance of the research.

Although pancreaticoduodenectomy (PD) outcomes have improved, it remains a procedure with a high perioperative complication rate. Surgical site infection (SSI) is one of the most common complications after PD. In a retrospective review of all patients who underwent PD at Johns Hopkins between 9/2011-8/2014, a total of 679 patients, 30-day SSI was observed in 16.7%. By univariate analysis, perioperative blood transfusion, operative time greater than 7 hours, pre-operative chemotherapy and/or radiation, bile stent, absence of a superficial wound vacuum closure device, and vascular resection were associated with SSI (all, $p < 0.05$). On multivariable analysis, pre-operative bile stent/drain and neoadjuvant chemotherapy were independent predictors of SSI (all, $p < 0.001$). Studies in colorectal patients have found an estimated cost of up to \$1400 per patient secondary to prolonged hospitalization, wound care, and wound complications in patients with procedures complicated by a SSI. Furthermore, in another study of 1144 patients undergoing PD between 1995 and 2011 at Johns Hopkins Hospital, post-operative complications delayed time to adjuvant therapy, decreased median survival.¹

Our hypothesis is that placement of Prevena Peel & Place Dressing using the standard KCI VAC after suture on patients undergoing PD at highest risk of infection will result in a significant decrease in SSI rate. We plan to perform a randomized control trial where patients who have had pre-operative bile stent/drain placement and/or neoadjuvant chemotherapy will undergo closure with Prevena Peel & Place Dressing using the standard KCI VAC after suture versus standard closure. We will then follow these patients for 30 days post-operatively to determine SSI and other peri-operative complication rate.

2. Objectives (include all primary and secondary objectives)

Primary objective:

To evaluate the effectiveness of Prevena Peel & Place Dressing using the standard KCI VAC after suture closure versus standard closure at reducing wound infections in patients undergoing pancreaticoduodenectomy

Secondary objective:

To evaluate the impact of Prevena Peel & Place Dressing using the standard KCI VAC after suture on hospital length of stay, readmission, and time to adjuvant therapy

3. Background (briefly describe pre-clinical and clinical data, current experience with procedures, drug or device, and any other relevant information to justify the research)

Although pancreaticoduodenectomy (PD) outcomes have improved, it remains a procedure with a high perioperative complication rate. Surgical site infection (SSI) is one of the most common complications after PD. In a retrospective review of all patients who underwent PD at Johns Hopkins between 9/2011-8/2014, a total of 679 patients, 30-day SSI was observed in 16.7%. By univariate analysis, perioperative blood transfusion, operative time greater than 7 hours, pre-operative chemotherapy and/or radiation, bile stent, absence of a superficial wound vacuum closure device, and vascular resection were associated with SSI (all, $p < 0.05$). On multivariable analysis, pre-operative bile stent/drain and neoadjuvant chemotherapy were independent predictors of SSI (all, $p < 0.001$). Studies in colorectal patients have found an estimated cost of up to \$1400 per patient secondary to prolonged hospitalization, wound care, and wound complications in patients with procedures complicated by a SSI. Furthermore, in another study of 1144 patients undergoing PD between 1995 and 2011 at Johns Hopkins Hospital, post-operative complications delayed time to adjuvant therapy, decreased median survival.¹

Our hypothesis is that placement of Prevena Peel & Place Dressing using the standard KCI VAC after suture on patients undergoing PD at highest risk of infection will result in a significant decrease in SSI rate. We plan to perform a randomized control trial where patients who have had pre-operative bile stent/drain placement and/or neoadjuvant chemotherapy will undergo closure with Prevena Peel & Place Dressing using the standard KCI VAC after suture versus standard closure. We will then follow these patients for 30 days post-operatively to determine SSI and other peri-operative complication rate.

Our institution has extensive experience with using this product for the prevention of SSI in patients undergoing surgery over the past several years, most specifically after ventral hernia repair. Superficial wound vacuum closure has been shown in a previous study by our group to decrease SSI from 32% to 9% ($p < 0.001$) and surgical site occurrence (SSO) from 42% to 17% ($p < 0.001$) in patients undergoing ventral hernia repair. Furthermore, when used in grade 3 ventral hernias, superficial wound vacuum closure had an SSI rate of 5.2% and an SSO of 20.7% at 90 days, which is lower than previously published rates using standard closure in these complex hernia repairs. All surgeons who will participate in this study have familiarity with the use of the wound vacuum device after surgical closure.

4. Study Procedures

- a. Study design, including the sequence and timing of study procedures (distinguish research procedures from those that are part of routine care).

All patients who are planned to undergo pancreaticoduodenectomy at Johns Hopkins Hospital will be assessed for eligibility and enrolled. Members of the department of surgery who are listed as the team members will be responsible for approaching the participants. Patients will be screened for eligibility. Only patients who have received neoadjuvant therapy and/or have undergone biliary stent placement will be approached. In addition patients will also be screened for known allergies to silver or acrylic adhesives.

Date: April 10, 2018

Principal Investigator: [name]

Application Number: IRB00109564

Recruitment will take place in the (i) surgical clinics, or (ii) at the pre-operative evaluation clinics prior to the surgery. Recruitment process will be mindful of patient privacy issues.

Discussions will be held by the potential participant's clinical and will not likely involve any additional patient protected health information beyond what is already required for the standard medical care. A written consent will be taken from these patients. The patients who are suitable candidates for the study will be approached in a clinical setting that is surgical clinics, preoperative assessment clinics, etc.

Those members of the research team (principal investigator, co-investigator, research nurse) who consent patients have been trained in informed consent procedures, are familiar with the protocol, and are listed as a consentor in the application document. Patients are given adequate time and privacy to consider the research study. Before the patient signs the consent, the consentor must be satisfied that the participant understands the information provided, has had an opportunity to discuss the information and ask questions, and is aware that he/she may withdraw from the study at any time.

A copy of the signed consent form will be provided to the patients at time of consent. Contact information will be provided to these patients so that they can contact the study team in the future, if they have any questions regarding the study.

Once consented, these patients will be entered into CRMS.

All consented patients will undergo the same standard PD. At the time of closure the patients will be randomized to either standard closure or closure using the Prevena Peel & Place Dressing using the standard KCI VAC after suture closure.

The device will be left in place for 4 days after surgery. As part of the patients' clinical evaluation the surgical wound site will be inspected daily by the surgical team. If there are signs of infections the device will be removed. All patients will have their device removed prior to discharge.

The patients will be evaluated for wound infection during their hospital stay and also during their outpatient follow-up for up to 30 days after surgery. The CDC guidelines will be used to diagnose SSIs.

All patients will be followed for 30 days to collect data on SSI and other post-operative complications.

In total we plan to consent 144 patients for this study – 72 patients in the Prevena Peel & Place Dressing using the standard KCI VAC after suture closure arm, and 72 patients in the standard control arm.

b. Study duration and number of study visits required of research participants.

The study duration will be approximately 2 years. The patients will not require additional research visits.

5. Inclusion/Exclusion Criteria

Inclusion Criteria:

1. Patient to undergo pancreaticoduodenectomy for a pancreatic tumor at the Johns Hopkins Hospital
2. Patient treated with neoadjuvant chemotherapy with or without radiation therapy prior to surgical resection, AND/OR placement of a biliary stent and/or drain for biliary tree decompression

Exclusion Criteria:

1. Age 18 years or younger
3. Laparoscopic or robotic pancreaticoduodenectomy
4. Patient did not undergo either placement of a preoperative biliary stent/drain or neoadjuvant chemotherapy with or without radiation therapy.
5. All patients who are have known allergies or are sensitive to silver and acrylic adhesives.

6. Drugs/ Substances/ Devices

- a. The rationale for choosing the drug and dose or for choosing the device to be used.
Our institution has extensive experience with using this product for the prevention of SSI in patients undergoing surgery over the past several years, most specifically after ventral hernia repair. Superficial wound vacuum closure has been shown in a previous study by our group to decrease SSI from 32% to 9% ($p < 0.001$) and surgical site occurrence (SSO) from 42% to 17% ($p < 0.001$) in patients undergoing ventral hernia repair. Furthermore, when used in grade 3 ventral hernias, superficial wound vacuum closure had an SSI rate of 5.2% and an SSO of 20.7% at 90 days, which is lower than previously published rates using standard closure in these complex hernia repairs.

7. Study Statistics

- a. Primary outcome variable.
The primary outcome variable is surgical site infection (SSI) rate
- b. Secondary outcome variables.
The secondary outcome variables are hospital length of stay, readmission rate, and time to adjuvant chemotherapy
- c. Statistical plan including sample size justification and interim data analysis.
The primary outcome variable, SSI rate, will be analyzed using a chi-square test. The secondary outcome variable of hospital length of stay will be analyzed using a t-test if the data are normally distributed or a ranksum test if they are not. The secondary outcome variable of readmission rate will be analyzed using a chi-square test. The secondary outcome variable of time to adjuvant chemotherapy will be analyzed using survival analysis methods, including Kaplan-Meier curves and log-rank test.

Prior data from our institution has demonstrated that the risk of a surgical site infection after pancreaticoduodenectomy is 30% if the patient either underwent neoadjuvant chemotherapy or had a biliary stent/drain placed before surgery. This study has been powered to show a decrease in SSI rate from 30% to 10%, and thus would necessitate 72 patients in each arm of the trial (Open Epi software, with Fleiss continuity correction).

Interim data analysis will only performed to monitor for futility, as described below.

Date: April 10, 2018

Principal Investigator: [name]

Application Number: IRB00109564

d. Early stopping rules.

We will perform an interim analysis when SSI results are available for the first 36 patients in each group. Conditional power calculations will be performed according to the method proposed by Proschan, Lan, and Wittes (2006), assuming that the results seen up until the interim analysis continue until the end of the trial (empirical conditional power). If the conditional power under the empirical assumption is less than 0.50, the trial will be terminated for futility.

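### Randomizing at closure against an undefined standard closure lets wound closure differ by arm, so the dressing's effect on SSI may not be separable from closure technique

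*Combined protocol and SAP*

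**What the plan says.** All references are to the combined protocol and SAP.

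- **Timing and arms (section 4a).** "At the time of closure the patients will be randomized to either standard closure or closure using the Prevena Peel & Place Dressing". The sentence goes on to specify the KCI VAC over a sutured wound. The arms are thus named as kinds of closure and assigned when closure takes place.
- **Primary objective (section 2).** The contrast is "Prevena Peel & Place Dressing using the standard KCI VAC after suture closure versus standard closure". The Abstract and Background put it similarly: patients "will undergo closure with Prevena Peel & Place Dressing using the standard KCI VAC after suture versus standard closure".
- **Control arm.** Section 4a calls it "72 patients in the standard control arm". Closure material, technique and control dressing are not defined anywhere.
- **What is common to both arms (section 4a).** "All consented patients will undergo the same standard PD". This covers the operation. It comes immediately before the sentence that divides closure by arm.
- **What the hypothesis credits (Abstract and Background).** The hypothesis opens: "Our hypothesis is that placement of Prevena Peel & Place Dressing using the standard KCI VAC after suture on patients undergoing PD". It predicts a lower SSI rate in these high-risk patients. The intended inference is about the dressing.
- **Analysis (section 7c).** The primary test is a chi-square test of SSI, with no adjustment for closure method and no plan to record it.

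**The concern.** The dressing goes on after the wound has been sutured, so nothing about the device requires the arm to be known before then. Yet the plan assigns the arm at the closure step and describes the closures differently: suture is specified for the device arm only.

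The surgeon cannot be blinded to the device. A surgeon who knows the arm while closing could use a different technique in controls, or take more or less care with the wound. Closure is the operative step nearest to the SSI endpoint, and expectations are unlikely to be neutral, because section 3 reports the group's own fall in SSI from 32% to 9% with this type of device in hernia repair.

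A less protective control closure would make the dressing look better than it is. Extra care in controls would hide a real benefit. Either would be mixed into the arm difference, and because closure method is not recorded, the mixing could not be examined afterwards.

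**Working it through.** **1. The plan's own figure.** Section 7c gives SSI rates of 30% and 10%, 72 per arm, with the Fleiss continuity correction. Alpha, sidedness and power are not stated; I assume two-sided 5% and 80%.

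- Uncorrected: n = [1.960·√(2·0.20·0.80) + 0.842·√(0.30·0.70 + 0.10·0.90)]² / 0.20² = [1.109 + 0.461]² / 0.04 = 61.6, so 62.
- Corrected: n′ = (61.6/4)·[1 + √(1 + 4/(61.6·0.20))]² = 15.4·(2.151)² = 71.2, so 72.

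The stated 72 reproduces. Nothing below changes it.

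**2. The text, arm by arm.**

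| | Device arm | Control arm |
|---|---|---|
| Operation | same PD | same PD |
| Closure | suture | standard, undefined |
| Dressing | Prevena with KCI VAC | not described |
| Arm assigned | at closure | at closure |
| Closure method recorded or adjusted for | no | no |

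Only the operation is stated to be common. The dressing row is the intended difference. The closure row may or may not be a second one.

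**3. False benefit if control closure shifts the control rate.** Assumptions: the dressing does nothing, SSI is 30% in the device arm, 72 per arm, uncorrected chi-square at two-sided 5%. The probability is the sum, over all pairs of event counts that are significant with fewer events in the device arm, of Bin(x; 72, control rate) × Bin(y; 72, device rate).

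| Control SSI | Device SSI | P(significant, favouring device) |
|---|---|---|
| 30% | 30% | 0.025 |
| 35% | 30% | 0.092 |
| 40% | 30% | 0.237 |

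**4. Lost power if closure care lowers the control rate.** The dressing works as planned (10%).

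| Control SSI | Device SSI | Power |
|---|---|---|
| 30% | 10% | 0.874 |
| 25% | 10% | 0.677 |
| 20% | 10% | 0.394 |

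**5. The same question with the control rate held at the planned 30%.** Suppose a fraction f of controls is closed by another method with SSI risk ratio r against suture, and the dressing does nothing. The device-arm rate is then 0.30 / [(1 − f) + f·r]. Probabilities here use the normal approximation.

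| f | r | Device SSI | Spurious difference | P(significant, favouring device) |
|---|---|---|---|---|
| 0 | any | 30% | 0 | 2.5% |
| 0.25 | 1.25 | 0.30/1.0625 = 28.2% | 1.8 points | 4% |
| 0.5 | 1.5 | 0.30/1.25 = 24% | 6 points | 12.5% |
| 1 | 1.5 | 0.30/1.5 = 20% | 10 points | 28% |
| 1 | 2 | 0.30/2 = 15% | 15 points | 58% |

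The documents give no SSI rate by closure technique, so f, r and the shifts in steps 3 and 4 are all assumptions.

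**The case against.** The strongest reply is that the plan describes an add-on to ordinary closure. At a single hospital, standard closure may well be the same suture closure, done alike in both arms. The contrast then isolates the dressing and the artefact is zero. The documents neither confirm nor exclude this. If the closure is the same in kind, the question of technique falls away, but the surgeon could still know the arm while closing.

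Two stronger readings are tempting and are not supported.

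- *A reader might infer that the arm is revealed before the skin is closed.* This is the natural reading of section 4a, but the text does not place allocation before or after fascial or skin closure, and section 3 speaks of using the device once surgical closure is done.
- *A reader might infer that an SSI difference could not be credited to the dressing at all.* That would need closure actually to differ by arm in a way that affects SSI. Even then, the comparison named in the primary objective remains a valid randomized comparison of two strategies. Only attribution to the dressing alone weakens.

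The size is also open to challenge. The 35% and 40% scenarios move the control arm off its planned 30%. A rise from 30% to 40% needs every control closed by a method with risk ratio 1.33 (40/30), or half of them at 1.67 (0.5 + 0.5·1.67 = 1.33). Nothing in the documents suggests either. The mild case in step 5 moves 2.5% only to 4%. This stands: the figures show sensitivity and do not estimate bias.

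**Conclusion.** The point holds as a gap in the design, not as a demonstrated bias. Allocation is made at closure, suture is specified for one arm only, the control closure is undefined, and nothing makes closure common or withholds the arm until closure is complete. Closure technique or care may therefore differ by arm, and the dressing effect may not be separable from it.

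Neither size nor direction can be derived from the documents. Under assumed 5 or 10 point upward shifts in the control rate with no dressing effect, the chance of a false benefit goes from 2.5% to 9% or 24%. Under equal downward shifts with the planned effect, power goes from 87% to 68% or 39%. If closure is the same in both arms, there is no change. These figures rest on 72 per arm and a two-sided 5% uncorrected chi-square test; section 7c states neither the level nor whether the test is corrected.

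This is more than a missing definition, because the moment of allocation is a stated step that can be moved at little cost.

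**What to change.** 1. **Section 4a, order of steps.** State that the surgeon closes the incision by the method used for all trial patients, that the allocation is opened only after this, and that the patient is then randomized to the Prevena dressing with the KCI VAC or to the standard dressing.
2. **Sections 2 and 4a, wording of the arms.** Reconcile the suture closure of the device arm with the standard closure of the control arm, so that both arms name the same closure. The technique is for the sponsor to choose.
3. **Data collection.** Record the closure method in every patient and report it by arm. With closure completed before allocation, it becomes a pre-randomization characteristic, so any remaining variation is balanced by randomization on average.

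The cost is protocol wording, one recorded item, and an allocation opened a few minutes later in the same operation. There are no added visits, and 72 per arm is unchanged. Surgeons lose the freedom to vary closure by arm. The change does not deal with postoperative wound care, which stays unblinded.

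### Does a target of 144 consented patients leave the trial short of 72 per arm?

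*Combined protocol and SAP*

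**What the plan says.** Section 4a sets the total: "In total we plan to consent 144 patients for this study – 72 patients in the Prevena Peel & Place Dressing", and it completes the split with "72 patients in the standard control arm".

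The same section places consent and allocation at different times. On consent: "Recruitment will take place in the (i) surgical clinics, or (ii) at the pre-operative evaluation clinics prior to the surgery". On allocation: "At the time of closure the patients will be randomized to either standard closure". Between the two it says "All consented patients will undergo the same standard PD", while the consent paragraph has the consentor confirm that the participant "is aware that he/she may withdraw from the study at any time".

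Section 7c derives the size from a fall in SSI rate from 30% to 10%, using OpenEpi with the Fleiss continuity correction, and concludes that this "thus would necessitate 72 patients in each arm of the trial". Section 7d times the interim analysis by group: "when SSI results are available for the first 36 patients in each group". The documents contain no allowance for loss before randomization and no replacement rule.

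**The concern.** A power calculation concerns patients in the comparison, and consent comes earlier. Patients can drop out in between: they may withdraw, or the operation may be done laparoscopically or robotically, which Section 5 excludes. A team that stopped at 144 signed forms would randomize fewer than 144 unless nobody was lost.

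The 72 per arm has almost no slack, because it is the formula result rounded up to the next whole patient. On the literal reading every loss before closure comes straight off the planned size, and the stated sample size would not be the one delivered. At stake would be some power for the primary SSI comparison. Bias is not at issue, since patients lost before randomization were never in either arm.

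**Working it through.** **1. Reproduce the plan's figure.** Inputs from Section 7c: p1 = 0.30, p2 = 0.10, equal arms, Fleiss correction. The plan states neither alpha nor power. Two-sided 5% and 80% power are assumed because they reproduce its figure.

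- Mean rate 0.20, difference d = 0.20, z-values 1.960 and 0.8416.
- Uncorrected: n' = [1.960 × √(2 × 0.20 × 0.80) + 0.8416 × √(0.30 × 0.70 + 0.10 × 0.90)]² / d² = (1.1087 + 0.4610)² / 0.04 = 61.60, so 62 per arm.
- Fleiss: n = (n'/4) × [1 + √(1 + 4/(n'd))]² = 71.25, so 72 per arm.

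The 72 is reproduced and contains no inflation for loss. It is therefore a number of patients in the arms.

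**2. Decide which event the 144 refers to.**

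| Place | Unit counted |
|---|---|
| 4a, the verb | consents |
| 4a, same sentence after the dash | 72 in each arm |
| 4a, preceding paragraphs | every consented patient has the operation and is randomized at closure |
| 7c | 72 in each arm |
| 7d | first 36 in each group, half of 72 |

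A patient belongs to an arm only after randomization, so 72 plus 72 in arms means 144 randomized. Only the verb points the other way. Section 4a treats consented and randomized patients as the same people, which explains how the verb came to be used.

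**3. Size the literal reading anyway.** Suppose consents were capped at 144 and a fraction L were lost before closure, leaving about 72 × (1 − L) per arm. The loss rates are assumptions. Exact power sums the two binomial distributions (0.30 and 0.10) over every pair of counts at which the chi-square statistic exceeds 1.960².

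| Assumed loss | About n per arm | Uncorrected chi-square | Continuity-corrected |
|---|---|---|---|
| 0% | 72 | 87.4% | 81.6% |
| 5% | 68 | 85.1% | 80.0% |
| 10% | 65 | 83.2% | 77.5% |
| 15% | 61 | 81.0% | 74.0% |
| 20% | 58 | 79.7% | 71.0% |

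Exact power is not monotone in n, so it was also averaged over a binomial number randomized out of 144. At 5/10/15/20% loss the averages are 85.5/83.3/81.2/78.9% uncorrected and 79.4/77.0/74.1/70.9% corrected.

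The uncorrected test gives 80.5% at 59 per arm and stays above 80% at every size from 59 to 72. Reaching 59 means losing 13 of 72 per arm, or 18%. Losing one patient per arm (72 to 71) moves it from 87.4% to 86.8%.

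**4. What recruiting to 144 randomized would take.** Consents needed are 144 / (1 − L): 152, 160, 170 and 180 at the same four assumed losses. On the intended reading the price of loss is a somewhat longer consenting period, and power is unaffected.

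**The case for a change.** The strongest opposing case is that a study team works from the protocol, and the only overall total it gives is a count of consents. The statement that all consented patients undergo the operation is in effect an assumption of zero loss. No figure supports it, and it stands beside a right to withdraw at any time. A literal-minded team could stop early. If the final test were continuity-corrected, as the sample size was, average power would already be 79.4% at an assumed 5% loss.

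Part of this stands. The verb is inexact, no loss allowance or replacement rule is written, and 72 has no margin. The shortfall itself does not follow. It needs a cap on consents, which the plan never sets, together with a loss rate that the plan does not give. The corrected-test figures also need a continuity correction in the analysis, and Section 7c attaches the correction only to the sample size. A replacement rule matters only if there is a cap. When the target is 72 per arm, a patient lost before closure never counted towards it, and consenting simply continues.

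**Conclusion.** No change to the plan is needed. Section 4a uses the wrong verb for a target that its own sentence, Section 7c and Section 7d all express per arm. The unwritten rule, to keep consenting until 72 are randomized to each arm, is one that any trial team would supply. On that reading the shortfall is zero.

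On the less likely reading of 144 consents as a ceiling, the uncorrected chi-square test keeps at least 80% exact power up to about 18% loss. This rests on the planned rates of 30% and 10%, and on a two-sided 5% level and an 80% benchmark inferred from the match to 72. All loss rates are assumptions. Design, endpoint and analysis are the same under either reading.

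### Do "wound infection" in the objective and "SSI" in the primary outcome and sample size leave the primary event undefined?

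*Combined protocol and SAP*

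**What the plan says.** The document uses two terms for the infection it aims to prevent.

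- Section 2, primary objective: the comparison is with "standard closure at reducing wound infections in patients undergoing pancreaticoduodenectomy".
- Section 4a, assessment: "The patients will be evaluated for wound infection during their hospital stay", with outpatient checks continuing to day 30. Directly after that comes "The CDC guidelines will be used to diagnose SSIs", and the paragraph after it says "All patients will be followed for 30 days to collect data on SSI and other post-operative complications".
- Section 7a: "The primary outcome variable is surgical site infection (SSI) rate", with no infection classes and no time window in that section.
- Section 7c: "Prior data from our institution has demonstrated that the risk of a surgical site infection after pancreaticoduodenectomy is 30"% in patients with neoadjuvant chemotherapy or a biliary stent or drain. The trial is powered for a fall to 10% with 72 per arm, using OpenEpi with the Fleiss continuity correction. Alpha, sidedness and power are not given.
- Section 7d: the futility look at 36 patients per group uses SSI results.

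SSI is also the term in the trial title and in the hypothesis (sections 1 and 3).

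**The concern.** Read strictly, the objective and the bedside assessment concern the wound, while the outcome and planning rates concern the surgical site. If the second is the wider category, an infection away from the incision might be a primary event under section 7a but fall outside the objective in section 2. Section 4a collects SSI together with other complications and does not say where such an infection belongs. The only examination it describes is daily inspection of the wound.

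Two things would be at stake. An assessor might have to decide case by case what enters the primary count. And if the 30% counted a different set of infections from the endpoint, 72 per arm would no longer fit the endpoint analysed, and the futility look would rest on the same uncertain event. The reader cannot settle this from the document, because the source of the 30% is given only as prior institutional data.

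**Working it through.** **Where each term is used.**

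| Place | Term |
|---|---|
| Title; hypothesis (sections 1, 3) | SSI |
| Primary objective (section 2) | wound infections |
| Assessment (section 4a) | wound infection, then SSI by CDC guidelines in the next sentence |
| Data collection, 30 days (section 4a) | SSI |
| Primary outcome (section 7a) | SSI |
| Test, 30% and 10% rates (section 7c) | SSI |
| Interim look (section 7d) | SSI |

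Everything that determines the analysis uses SSI. The other term appears in the objective and in one sentence of section 4a, and that sentence is followed directly by the rule for diagnosing SSI. The natural reading is that the terms are synonyms. On that reading the primary event is an SSI by CDC guidelines within 30 days of surgery.

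**The plan's own figure.** Inputs: p1 = 0.30, p2 = 0.10 and the Fleiss correction, from section 7c. Assumed: two-sided 5% (z = 1.960) and 80% power (z = 0.842).

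With d = 0.20 and mean rate 0.20, the uncorrected number per arm is

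n' = [1.960·√(2·0.20·0.80) + 0.842·√(0.30·0.70 + 0.10·0.90)]² / 0.20² = 61.6.

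The correction gives

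n = (n'/4)·[1 + √(1 + 4/(n'·d))]² = 15.4·[1 + √1.325]² = 71.2, rounded up to 72.

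This matches the protocol. Power on the same corrected scale is

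Φ{[d − 1/72 − 1.960·√(2·0.20·0.80/72)] / √[(0.21 + 0.09)/72]} = Φ(0.0554/0.0645) = 0.80.

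Without the correction, power at 72 is 0.86 by the normal approximation and 0.87 by exact binomial calculation for the chi-square test.

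**What a mismatch would do, if there were one.** Let q be the percentage points of infection away from the incision. The documents give no value, so q is an assumption. So are the one-third risk ratio applied to wound infections in A and B, and the unchanged q points in B and C. N per arm and power at 72 are both continuity-corrected.

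| Reading | q | Rates | N per arm | Power at 72 |
|---|---|---|---|---|
| Endpoint and planning rates match as planned | – | 30% vs 10% | 72 | 0.80 |
| A: 30% is all SSI, only wound infections counted | 3 | 27% vs 9% | 82 | 0.74 |
| A | 6 | 24% vs 8% | 94 | 0.67 |
| B: all SSI counted at 30%, dressing acts on the wound part only | 3 | 30% vs 12% | 90 | 0.69 |
| B | 6 | 30% vs 14% | 117 | 0.56 |
| C: 30% to 10% is wound only, all SSI counted | 5 | 35% vs 15% | 83 | 0.74 |
| C | 10 | 40% vs 20% | 91 | 0.69 |

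The treatment rate in B is q plus one third of (30 − q): for q = 3, 3 + 9 = 12; for q = 6, 6 + 8 = 14.

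The losses would matter if q were known to be of this size. But A and C both need the planning rate and the endpoint to count different things, although the document gives them the same name. B involves no mismatch of definitions. It questions whether 10% is attainable, which is a matter of effect size and not of which infections count.

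**The case for a change.** The best case for a change is that naming a diagnostic standard tells the assessor how to recognise an SSI, not which SSIs enter the primary count, and that no edition or class is named. Two sentences, one in section 7a and one in section 7c, would remove the doubt before any outcome is classified. The 30% cannot be checked: the only data set described gives 16.7% 30-day SSI in 679 patients, and no count is shown for the higher-risk subgroup. The same event also feeds the futility rule, so an informal decision on definition could affect stopping as well as the final test.

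Part of this stands. The classes are not listed, the definition and window behind the 30% are not given, and saying so would do no harm. The rest does not lead to a correction. Where an outcome is defined by an outside standard and no class is excluded, the ordinary course is to count whatever meets the standard. The 16.7% covers all pancreaticoduodenectomy patients and the 30% a higher-risk group, so the two need not conflict. An uncheckable institutional planning rate is common and is not evidence of inconsistency. The one substantive alternative, restricting the primary event to the wound to follow the objective's wording, would be a trade-off: closer to where the dressing acts, but with fewer events and a departure from the outcome the plan names throughout.

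**Conclusion.** No change follows. This is loose wording and missing detail that analysts would fill sensibly, not an error in the plan. Followed as written, the primary event is an SSI by CDC guidelines within 30 days, compared by a chi-square test. The planned 72 per arm is right for 30% against 10%, given the inferred two-sided 5% and 80% power. No mismatch between endpoint and planning rate is shown. The corrected powers of 0.56 to 0.74 in the illustrations all rest on an assumed q for which the documents give no basis. Using one term throughout and confirming that the 30% and 10% refer to the same infections would be a courtesy to the reader. The conclusion would change only if the institutional data were found to have counted a different set of infections.
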